8.2 Safety assessments

Planned time points for all safety assessments are provided in the SoA.

8.2.1 Clinical safety laboratory assessments

See Table 8 for the list of clinical safety laboratory tests to be performed and to the SoA for the timing and frequency. All protocol-required laboratory assessments, as defined in the table, must be conducted in accordance with the laboratory manual and the SoA.

The Investigator should make an assessment of the available results with regard to clinically relevant abnormalities. The laboratory results should be signed and dated and retained at centre as source data for laboratory variables.

For information on how AEs based on laboratory tests should be recorded and reported, see Section 8.3.7.

Additional safety samples may be collected if clinically indicated at the discretion of the Investigator. The date, time of collection and results (values, units and reference ranges) will be recorded on the appropriate eCRF.

The clinical chemistry, haematology and hemostasis will be performed at a central laboratory. The urinalysis will be performed at a local laboratory.

Table 8 Laboratory safety variables

Haematology/Haemostasis (whole blood)	Clinical Chemistry (serum)
B-Haemoglobin	S-Creatinine
B-Leukocyte count	S-Bilirubin, total
B-Leukocyte differential count (absolute count)	S-Alkaline phosphatase (ALP)
B-Platelet count	S-AST
B-Red blood cell	S-ALT
B-Hematocrit	S-Albumin
B-Mean corpuscular volume	S-Potassium
B-Mean corpuscular hemoglobin concentration	S-Calcium
	S-Sodium
Coagulation	S-Chloride
Prothrombin time (screening only)	S-Gamma glutamyl transferase

Activated partial thromboplastin time (screening only)	S-Blood urea nitrogen
	S-Glucose
U-Urinalysis	S-Bicarbonate
Colour/Appearance	beta-hydroxybutyrate
Specific gravity	
potential of hydrogen	
Protein	
Glucose	
Ketones	
Blood	
Leucocyte esterase	
Bilirubin	
Urobilinogen	
Nitrite	

Notes: Tests for AST, ALT, ALP, and total bilirubin must be conducted concurrently and assessed concurrently. Urinalysis for specific gravity, pH, protein, glucose, ketones, blood, leucocyte esterase, bilirubin, urobilinogen, and nitrite may be performed at the site using a licensed test (dipstick).

NB. In case a subject shows an AST or ALT $\geq 3xULN$ together with total bilirubin $\geq 2xULN$ please refer to Appendix E ‘Actions required in cases of increases in liver biochemistry and evaluation of Hy’s Law’, for further instructions.

Other Tests

- Calcitonin (screening only), thyroid-stimulating hormone (screening only), pancreatic amylase, lipase
- Blood lactate
- HbA1c
- Anti-drug antibodies
- Total immunoglobulin (Ig) and subsets (Ig A/E/G/M)
- Urine or serum (human chorionic gonadotropin) pregnancy test (females only)
- Hepatitis B surface antigen, hepatitis C antibody (screening only)
- Glucose metabolism panel for MMT: Timed glucose, insulin, pro-insulin, c-peptide, GLP-1, and glucagon.
- Fructosamine

- Fasting lipid profile: HDL-C, LDL-C, TG, and FFA
- TG

8.2.2 Physical examinations

A complete physical examination will be performed and include an assessment of the following: general appearance, respiratory, cardiovascular, abdomen, skin, head and neck (including ears, eyes, nose and throat), lymph nodes, thyroid, musculo-skeletal (including spine and extremities) and neurological systems.

Targeted examinations (evaluation of selective body systems at the judgement of the physician or qualified designee based on subject presentation) are sufficient for the remaining time points after the screening.

Physical examination will be performed at timelines as specified in the SoA, Investigators should pay special attention to clinical signs related to previous serious illnesses, new or worsening abnormalities may qualify as adverse events, see Sections 8.3.6 and 8.3.7 for details. Height will be measured at screening.

8.2.3 Vital signs

- Axillary temperature, pulse rate, respiratory rate, and blood pressure will be assessed.
- Blood pressure and pulse measurements will be assessed in the supine position for at least 10 minutes with a completely automated device. Manual techniques will be used only if an automated device is not available.
- Blood pressure and pulse measurements should be preceded by at least 10 minutes of rest for the subject in a quiet setting without distractions (e.g., television, cell phones).
- Vital signs (to be taken before blood collection for laboratory tests) will consist of 1 pulse and 3 blood pressure measurements (3 consecutive blood pressure readings will be recorded at intervals of at least 1 minute). The average of the 3 blood pressure readings will be recorded on the eCRF.
- ABPM will be used for the 24-hour period at Visit 2 (as a baseline) and at Visit 10, Visit 12 after receipt of the SC dose at the clinic visit.
- The subject should do a Ketostix[®] test daily on non-clinic-visit days during the at-home self-administration period

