Note: Whenever vital signs, ECGs, and blood draws are scheduled for the same nominal time, the ECG should occur first, then vital signs, and blood draws should occur last. The timing of the ECGs and/or vital signs should be such that it allows the blood draw (e.g., for PK) to occur as close as possible to the scheduled time. Ten minutes of supine rest should precede these assessments.

a. Body weight measurement should be taken in the morning before breakfast.

- b. Randomization may occur on either Day -1 or Day 1 after all eligibility criteria were confirmed.
- c. There is a consent form with check boxes available for the genetic future research sample and the non-genetic future research sample. Only sample(s) which the subject has consented to collect will be taken. Samples should be taken at Visit 12 or Withdrawal visit.
- d. Digital ECGs will be captured on Day -1; and pre-dose and 6 hours (\pm 15 min) post-dose on Days, 1, 6, 13, 20 and 48. All ECGs should be printed.
- e. Vital Signs Schedule: On Day 1, vital signs are to be recorded predose, and at 30, 60 and 90 minutes, 2 and 4 hours postdose. From Visit 4 to 11, vital signs are to be recorded predose, Also, vital signs are to be taken at all PK time points.
- f. ABPM device will be fitted at a convenient time on the day stated and worn for 24 hours, and subjects will receive training from study site staff on how to fit and wear the device during the day and whilst sleeping. On Visit 10, the ABPM device should be fitted as soon as possible after the subject arrives at the unit that morning
- g. The subject should undergo a Ketostix[®] test daily on non-clinic-visit days during the at-home self-administration period; the subject will indicate whether the result is negative or positive in the Daily Diary, and be instructed to call the site if the result is positive.
- h. PK Sampling Schedule for MEDI0382:
Pre-dose PK sample will be collected on Days 1 to 6, 13, 20, 34 and 48.
Follow-up: 7 to 14 days after administration of the last dose in the study.
PK sample at follow-up will be taken on the same day as that for ADA sampling.

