dosing of MEDI0382 up-titrated to 200 µg (Cohort 4). MEDI0382 treatment was associated with a mean change of -32.78% in MMT glucose AUC_{0-4h} (90% CI -36.98, -28.57) vs 10.16% (90% CI 14.10, -6.21) in placebo, $p < 0.0001$, and a mean change of 3.84 kg from baseline in body weight (90% CI - 4.55, -3.12) vs 1.70 kg (90% CI -2.40, -1.01) in placebo, $p = 0.0008$. MEDI0382 treatment was associated with numerically greater mean reductions in MMT glucose AUC_{0-4h} and body weight vs placebo in all cohorts. There were no unexpected safety signals and no increases in systolic or diastolic blood pressure (BP). With respect to heart rate, a trend towards a mean change from baseline in the order of 10 bpm that appeared to be consistent across Cohorts 1 to 3 was observed during office based measurements. In Cohort 4 an increase in heart rate of 11.7 bpm on Day 13 was observed and it reduced to 6.9 bpm on Day 41. Dosing was associated with increased gastrointestinal (GI) adverse events (AEs) with 40 vomiting related AEs observed in 8 (32%) subjects on MEDI0382 in Cohort 4, however the number of events diminished in frequency with dose up-titration. Tolerability was comparable to marketed GLP-1 receptor agonists. A Phase I, randomized, blinded (investigators and the subjects were blinded to the treatment assignment and the sponsor was unblinded to the treatment assignment) study (D5670C00012) to evaluate the safety, tolerability, PK, and immunogenicity of MEDI0382 administered as single SC doses to preobese/obese but otherwise healthy adult male and female subjects of Japanese and Chinese descent was finished (CSR preparation is ongoing). In Part A, 24 subjects of Japanese descent across 3 cohorts (8 subjects in each cohort) received single SC doses of 50 µg, 100 µg, and 150 µg of MEDI0382 or placebo in a 3:1 ratio. In Part B, approximately 8 subjects of Chinese descent received a single SC dose of 100 µg MEDI0382 or placebo in a 3:1 ratio. Increased GI adverse events (nausea, vomiting, etc.) were observed at the 150 µg dose level, which resulted in halting planned dose escalation to 200 µg. A higher proportion of subjects in the MEDI0382 group (6/24 subjects, 33.3%) than in the placebo group (1/6 subjects, 16.7%) had at least one TEAE, with vomiting, nausea, dizziness, and headache being the most frequent in the MEDI0382 group; the majority of these TEAEs occurred at the 150 µg dose level. All of the TEAEs were mild or moderate in severity. One subject (150 µg of MEDI0382) had atrioventricular block second degree; this was not deemed to be related to the investigational product. Increased heart rate was observed in 100 and 150 µg dose levels that follows the same pattern as reported previously, although a small number of patients experienced higher magnitude of changes in their heart rate from baseline in Study D5670C00002. In Study D5670C00011, in which dosing started from 50 µg and up-titrated to a maximum of 300 µg, there were no cases of arrhythmia reported. To date, there is no evidence to suggest the existence of a relationship between MEDI0382 dosing and clinically significant arrhythmia. Increase in heart rate was observed, consistent with what had been observed previously. No deaths or serious AEs were reported and no subject withdrew from the study due to AE. In conclusion, MEDI0382 was well tolerated in healthy male and female subjects of Japanese and Chinese descent. Overall, tolerability is comparable between studies D5670C00001 and

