3 OBJECTIVES AND ENDPOINTS

Table 5 Study objectives

Primary Objective:	Endpoint/Variable:
To characterise the safety profile and tolerability of MEDI0382 titrated up to a dose level of 100, 200 or 300 µg during dosing and follow-up	Measures of safety and tolerability (24-hour heart rate and blood pressure, other vital signs, ECG, laboratory test results, and AEs)
To assess the effects of MEDI0382 titrated up to a dose level of 100, 200 or 300 µg on glucose control and body weight versus placebo after 48 days of treatment	
 Percentage change in glucose AUC_{0-4h} as measured by a standardised MMT from baseline to the end of 48-day treatment Percentage change in body weight from baseline to the end of 48-day treatment
Secondary Objective:	Endpoint/Variable:
To assess the effects of MEDI0382 titrated up to a dose level of 100, 200 or 300 µg on additional measures of glucose control versus placebo after 48-day treatment	
 Change in HbA1c from baseline to the end of 48-day treatment Change in fasting plasma glucose from baseline to the end of 48-day treatment Change in fructosamine from baseline to the end of 48-day treatment
To assess the effect of MEDI0382 on glucose lowering during different meals and times of the day as measured by CGM	
 Change in percentage of time in hyperglycaemia (defined as > 7.8 mmol/L or > 140 mg/dL) and hypoglycaemia (defined as < 3 mmol/L or < 54 mg/dL) from the last day of baseline CGM over 24 hours to the end of dosing at each dose level (Days 5, 12, 19, and 47) Change in percentage of time in hyperglycaemia and hypoglycaemia at each dose level over 5 days for 50 µg and 7 days for other dose levels (Days 1 to 5, Days 6 to 12, Days 13 to 19, and Days 41 to 47)
To characterise the PK profile of 50, 100, 200 and 300 µg of MEDI0382	PK endpoint: Trough plasma concentration (C _{trough})
To characterise immunogenicity of 100, 200 and 300 µg of MEDI0382	Development of anti-drug antibodies and titre (if confirmed positive)
Exploratory Objective:	Endpoint/Variable:
To assess the effect of MEDI0382 on pancreatic and incretin hormone profiles at baseline and during the MMT	
 Change in insulin, GLP-1, and glucagon (AUC and levels) from baseline after 48-day treatment. Change in pro-insulin, c-peptide levels, pro-insulin/c-peptide ratio from baseline after 48-day treatment.

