4.2.2 Rationale for Endpoints

4.2.2.1 Rationale for Primary Endpoints

Safety and Tolerability

The goal is to ensure that repeated dosing with MEDI0382 shows acceptable safety profile for further clinical development, particularly with respect to GI AE profile and effect on heart rate (HR) and BP. Given the mechanism of action of MEDI0382, GI events including nausea, vomiting, abdominal bloating and diarrhea may be seen with increased frequency. Elevations in HR and alterations in BP may also be seen and effects on the QTcF interval will be evaluated.

Measures of Glucose Lowering and Weight Loss

Co-primary endpoints of glucose AUC and weight loss are adequate to evaluate the efficacy of up to 300 µg dose level to assess the benefit of a GLP-1 and glucagon receptor co-agonist for 48 days. Percentage change in weight will also be measured.

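### Section 8.2.3 takes one pulse but averages three blood pressures per session: a modest, cheaply avoidable loss of heart-rate precision at the sessions without ECG or ABPM

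*Protocol*

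**What the plan says.** Section 8.2.3 of the protocol sets the content of a vital-sign session: it "will consist of 1 pulse and 3 blood pressure measurements". It then adds: "The average of the 3 blood pressure readings will be recorded on the eCRF". Nothing comparable is said for pulse. Both variables are measured under the same conditions: "Blood pressure and pulse measurements will be assessed in the supine position for at least 10 minutes with a completely automated device".

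Section 4.2.2.1 names heart rate and blood pressure together among the main safety interests: "particularly with respect to GI AE profile and effect on heart rate (HR) and BP". Table 5 in Section 3 lists the primary safety variables: "Measures of safety and tolerability (24-hour heart rate and blood pressure, other vital signs, ECG, laboratory test results, and AEs". So 24-hour heart rate is named outright, and the clinic pulse enters under other vital signs. The safety objective in the same table extends over dosing and follow-up.

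On timing, Table 2 footnote e schedules Day 1 vital signs predose, at 30, 60 and 90 minutes, and at 2 and 4 hours. It continues: "From Visit 4 to 11, vital signs are to be recorded predose". Table 2 also marks vital signs on Day -1, Day 48 and at follow-up.

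**The concern.** The rule replicates one haemodynamic variable and leaves the other unreplicated, although both are named as particular concerns, and it gives no reason. Section 2.2 reports that the earlier multiple-dose study saw changes of about 10 bpm in office measurements. It adds: "In Cohort 4 an increase in heart rate of 11.7 bpm on Day 13 was observed", with a fall to 6.9 bpm by Day 41. Effects of that size are to be described here with 15 randomised subjects per arm.

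A single pulse carries the full within-session noise. In a change from baseline that noise enters twice, once at each end. Where no other heart-rate source is scheduled, nothing compensates. Follow-up is the clearest case: any description of heart rate returning towards baseline after the last dose rests on one pulse per subject.

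**Working it through.** The protocol states no SD, precision or power for heart rate, so there is no figure of its own to reproduce. The check has two parts.

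**1. Where is the single pulse the only scheduled reading?** Sources: Table 2 with footnotes d, e and f, and Sections 8.2.3, 8.2.4 and 8.2.5.1.

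| Vital-sign session | Triplicate ECG | 24-h ABPM |
|---|---|---|
| Day -1 | yes | yes (Visit 2) |
| Day 1 predose | yes | no |
| Day 1 at 30, 60, 90 min, 2 h, 4 h | no (next ECG at 6 h) | no |
| Days 2-5 predose | no | no |
| Days 6 and 13 predose | yes, also 6 h | no |
| Day 20 predose | yes, also 6 h | yes (Visit 10) |
| Day 34 predose | no | no |
| Day 48 | yes, predose and 6 h | yes (Visit 12) |
| Follow-up | no | no |

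The uncovered sessions number 5 + 4 + 1 + 1 = 11 of the 17 in Table 2. Where ABPM is worn, a 16-hour day and 8-hour night (an assumed split) give 16 × 4 + 8 × 2 = 80 pulse readings.

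**2. What would averaging three pulses gain?** All SDs here are assumptions. The within-session SD (sw) is 2-5 bpm, with independent readings, and k is the number of pulses averaged.

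- Measurement error of one session: sw/√k. From k = 1 to k = 3 the factor is 1/√3 = 0.58, a 42% reduction.
- Model A, visit-to-visit SD sb = 4-6 bpm: SD of change = √[2(sb² + sw²/k)].
- 95% CI half-width for an arm difference, 15 per arm: t(0.975, 28) × SD × √(2/15), with t = 2.048.

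Example, sb = 5 and sw = 4:
- k = 1: SD = √[2(25 + 16)] = 9.06; half-width 6.77 bpm.
- k = 3: SD = √[2(25 + 5.33)] = 7.79; half-width 5.83 bpm, 14% narrower.

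At sw = 3.5, the midpoint of the range, the narrowing is 1 − √(29.08/37.25) = 12%.

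Extremes:
- sb = 6, sw = 2: variance falls from 40 to 37.33 (7%), so the interval is 3% narrower.
- sb = 4, sw = 5: variance falls from 41 to 24.33 (41%), so the interval is 23% narrower.

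Model B lets true change differ between subjects, with SD sb = 6-10 bpm: SD of change = √(sb² + 2sw²/k). With sb = 8 and sw = 3, the SD goes from √82 = 9.06 to √70 = 8.37 and the half-width from 6.77 to 6.26 bpm, 7.6% narrower. Over the whole range the narrowing is 2.5-21.7%. The two models agree closely.

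**The case against.** The strongest reply is that heart rate is already well measured where it matters most. The heart-rate variable named in the primary safety endpoint is the 24-hour one, from dozens of ABPM readings. Triplicate ECGs cover baseline and the first day of each dose level. Section 2.2 puts median peak concentration at 4.5-9 h in one study and 6-8 h in another, so the 6 h ECG falls in the peak window. Most uncovered sessions are predose or before the peak. All of this stands, and it limits the scope of the point.

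A reader might infer that every by-visit heart-rate change is imprecise, or that a decline like the one in the earlier study could not be seen here. The protocol does not support either reading. Triplicate ECG heart rate on Days 13, 20 and 48, with ABPM on Days 20 and 48, allows an early-to-late comparison without Day 34, which adds only an intermediate point.

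Four further replies have weight:
- Sections 9.1 and 9.4.2 make safety descriptive, so no planned test or arm-difference interval depends on the pulse. The interval in the check is only a yardstick for precision.
- On Days 1-5 all three active groups receive 50 µg, so 45 against 15 could be compared. With t(0.975, 58) = 2.002 and √(1/45 + 1/15) = 0.298, the half-widths in the example become 5.40 and 4.65 bpm. Absolute imprecision is smaller there, but the relative gain is still 14%.
- Section 8.2.3 calls for measurement "with a completely automated device", but does not say that the device shows a pulse with each cuff reading. That is a plausible inference. The section also allows manual technique where no device is available.
- The rule is clear and contradicts nothing else in the protocol.

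What remains is that the listed sessions have no other scheduled heart-rate source, and that a descriptive summary also gains from less noisy data.

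**Conclusion.** The point holds as a minor one. At Day 1 from 30 min to 4 h, Days 2-5, Day 34 and follow-up, heart rate rests on one unreplicated pulse, while blood pressure in the same session is averaged over three readings. The result is a modest loss of precision in descriptive summaries. It introduces no bias, makes no stated figure wrong and affects no planned test.

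The size, roughly 3-23% on the width of an arm-difference 95% CI, rests wholly on assumed SDs and on independent readings within a session. The more subjects differ in true heart-rate response, the closer the gain lies to the lower end. The primary heart-rate variable from ABPM and the ECG heart rates are untouched.

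**What to change.** In Section 8.2.3, have the pulse recorded with each of the three blood pressure readings and the mean of the three entered on the eCRF, as is already done for blood pressure. Apply this at every session, including Day -1 and Day 1 predose, so that baseline and later values are measured in the same way.

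The cost is one sentence in the protocol and matching eCRF guidance, with no added visit or staff. It is free where the automated device shows a pulse with each reading, and takes a little effort where the manual fallback is used. If the sponsor prefers to keep one pulse, the protocol should at least say that ABPM and triplicate-ECG heart rate are the principal heart-rate measures and acknowledge the sessions they do not cover.

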8.2.4 Electrocardiograms

Triplicate 12-lead ECG will be obtained as outlined in the SoA (see Section 1.1) using an ECG machine that automatically calculates the heart rate and measures respiration rate, pulse rate, QRS, and QT intervals. Derived parameters (such as HR, QTcF and others as applicable) will be calculated.

At each time point at which triplicate ECG are required, 3 individual ECG tracings should be obtained in succession, no more than 2 minutes apart. The full set of triplicates should be completed within 5 minutes.

8.2.5 Other safety assessments

8.2.5.1 Ambulatory Blood Pressure Monitoring

Subjects will be given training at their local study site about how to set up and apply the ABPM device. In brief, an appropriate size cuff encircling 80% to 100% of the arm will be selected and the device will be fitted to the nondominant arm of the subject, with the bladder placed over the artery and an initial test reading performed. The subjects will be advised that for the first reading the device will inflate to a pressure of 180 mmHg, and thereafter the device will adapt to inflate to a pressure just above the last recorded BP. The subject will be advised to undergo normal daily activities while wearing the cuff, and he/she will be advised to avoid any strenuous form of activity, bathing, or showering while wearing the cuff. The subject will be advised to remain still during a measurement with the arm relaxed at heart level. The subject will also be given advice on how to wear the device during the day and at night while sleeping, and what to expect in terms of frequency of readings during the day (every 15 minutes) and overnight (every 30 minutes). During ABPM, systolic BP, diastolic BP, pulse pressure, pulse rate, and mean arterial pressure readings will be recorded over a period of 24 hours.

Data collected by ABPM device will be stored at the study site as source data. The data collected by ABPM device will be stored in a secure external media managed by the Sponsor. The Sponsor will regularly review integrity of the data provided by the study site. Frequency and procedure of the data provision by the study site as well as the procedure to review and manage the data by the Sponsor will be specified separately as a procedure manual.

8.2.5.2 Daily Diaries

On Day -1 (Visit 2), each subject will be trained on how to complete the Daily Diary according to the schedule outlined in SoA. Subjects will be encouraged to complete the Daily Diary as accurately as possible.

The following entries will be made daily into the Daily Diary and collected and reviewed by site staff at the appropriate visits:

- Date
- Confirmation that the acceptable temperature was maintained
- Unique kit number of dose
- Time of self-dose administration
- Start time of each meal

- Daily Ketostix[®] result (negative or positive) (Note: In case a Ketostix[®] [ketone] test result is positive, the subject will be instructed to call the site.)
- Any new medications or changes to standard medications (Note: Subjects will be instructed to contact the site in the event of any new medications or changes to medication.)
- Any vomiting and time of each episode
- Any other events

If the subject forgets to fill in any requested information, it will not be considered a protocol deviation.

